The observed event rates were extracted from each of the relevant studies and combined via a meta-analytic approach to arrive at an estimated historical AFS event rate for patients with no-option CLI. The pooled AFS rate estimate was calculated by taking the meta-analytic average using inverse variance weighting and a random-effects approach to account for the variability in the estimates and the potential heterogeneity of the studies. Confidence intervals around the pooled estimate were also calculated.

Table 4 shows details for each article included in the meta-analysis. The column labeled *Included Rutherford Categories* shows that many studies in Rutherford 4 (R4) as well as Rutherford 5 and 6 (R5, R6). The columns labeled *Observed Proportion R 5/6* shows the proportion of R5 and R6 patients in the study. Several studies did not report the proportion of R5 and R6, the proportion of patients in each Rutherford category, the proportion of high-risk patients was imputed based on the average of all studies that reported this proportion.

For studies only reporting patient classification by Fontaine Stage, and enrolled only Fontaine IV patients, it was not possible to determine the proportion of patients with Rutherford category four versus Rutherford category 5/6 disease. Some Fontaine IV patients would be classified as Rutherford category four because they did not meet both clinical and objective criteria for Rutherford category 5. The proportion of patients in each Rutherford category; the proportion of high-risk patients was, was also imputed based on the average of all studies that reported this proportion.

The proportions, either imputed or observed, are shown in the column labeled *Imputed or Observed Proportion R 5/6*.

The last column shows the risk-adjusted AFS rates. The risk adjustment was necessary since most studies reporting amputation-free survival in no-option CLI patients include subjects with R4, 5, and 6, and the OPG is based on R5/R6. Therefore, it was necessary to adjust the observed historical event rates to match that of the target patient population.

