The initial approach to determining the adjustment factor was to perform another literature search for papers reporting the hazard ratios (HR) for AFS, all-cause mortality, or major amputation by Rutherford category in patients with CLI (regardless of revascularization status). Thirteen publications were identified, but only 3 provided the unadjusted HR for Rutherford category 5/6 versus Rutherford category four patients. An adjustment factor for AFS rates was calculated from the HRs reported in Table 5 by the following methodology. First, the HR was log-transformed, and a weighted average of the log HR was calculated and then inverted back to the arithmetic scale. The resulting risk adjustment factor for AFS rates was 2.18.

The adjustment factor was then applied to the observed AFS rates in the applicable studies of no-option CLI patients according to the proportion of high-risk (Rutherford category 5/6) and low-risk (Rutherford category  $\leq 4$ ) patients in each study to arrive at an adjusted AFS rate by using the following three equations and solving for the High-Risk AFS rate:

**Equation 1:** *Adjustment Factor = Hazard Rate for death or major amputation for the high-risk patients  $\div$  Hazard Rate for death or major amputation low-risk patients = (1 - High-Risk AFS)  $\div$  (1 - Low-Risk AFS) = Low Risk AFS  $\div$  High Risk AFS*

**Equation 2** *Observed AFS Rate = High Risk % \* High Risk AFS + Low Risk % \* Low Risk AFS*

**Equation 3** *Low Risk AFS = High Risk AFS/adjustment*

The adjusted AFS rate for each paper is reported in the last column of Table 4.

The pooled AFS rate estimate was calculated by taking the meta-analytic average using inverse variance weighting and a random-effects model. This approach accounts for the variability in the estimates and the potential heterogeneity of the studies (see Meta-Analytic Average at the bottom of the last column in Table 4. Confidence intervals around the pooled estimate were also calculated. The meta-analytic estimate of the historical rate of AFS at six months in no-option patients with Rutherford category 5 or 6 CLI was 42.3% (95% CI, 33.5-51.1).

The performance goal is set at 54%, which is 2.9% higher than the upper 95% confidence limit of 51.1%.

**Table 4: Meta-analysis of 6-month AFS rate in no-option patients with Rutherford category 5 or 6 CLI (Original from Version 3.0 of Meta-Analytic Report)**

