**Table 5: Publications reporting unadjusted HR for Rutherford Category 5/6 v. Rutherford Category 4**

Study	N	Patient Risk Profile	Variable	Event	Unadjusted Hazard Ratio	95% CI
Chung et al. 2013	98	Rutherford 4/5/6	R 5/6 vs. R4	AFS	1.56	1.01 - 2.41
Soga et al. 2014	995	Rutherford 4/5/6	R 5 vs. R 4	Death	2.3	1.6 - 3.3
Spreen et al. 2016	281	Rutherford 4/5/6	Rutherford 5/6 vs. Rutherford 4	Major Amputation	2.03	1.28 - 3.21

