4 STUDY DESIGN OVERVIEW

This design utilizes a Bayesian Goldilocks² adaptive design for sample size determination. The pivotal cohort will consist of a minimum of 60 subjects and a maximum of 105 subjects. When N=60 subjects have been enrolled into this cohort, enrollment may stop based on a Bayesian predictive probability calculation of whether the study is likely to pass its primary endpoint hypothesis test. If enrollment does not stop, 15 more subjects will be enrolled (N=75 total in the pivotal cohort), and the process will be repeated. This may continue up to a maximum of N=105 subjects in the pivotal cohort. Once enrollment stops, 6 months of follow-up will ensue, at the end of which the one and only primary endpoint hypothesis test will occur.

The study was originally designed to enroll a maximum of 120 subjects rather than 105. After the N=90 but before the N=105 interim sample size assessments had occurred, it was determined that logistical and business constraints were forcing a mid-study revision of the maximum sample size to N=105. This SAP pre-specifies this change and discusses the statistical impact in Sections 6.6 and 6.7.

² Broglio KR, Connor JT, Berry SM., "Not too big, not too small: a goldilocks approach to sample size selection," *J Biopharm Stat.* 2014;24(3):685-705.

STATISTICAL ANALYSIS PLAN

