Stage IV	Necrosis and/or gangrene of the limb	III	5	Minor tissue loss – nonhealing ulcer; focal gangrene with diffuse pedal ischemia	Resting AP<60mmHg, ankle or metatarsal PVR flat or barely pulsatile; TP < 40mmHg
			6	Major tissue loss – extending transmetatarsally; functional foot no longer salvageable	

Studies that only used the Fontaine classification were compared to those that only used the Rutherford classification using logistic regression. The SAS code was:

```
proc logistic data=limlos_adj;
class study status class;
freq num;
model status(event='no event')= class;
run;
```

where status is whether there was a death or major amputation event at 6 months or not, the class was the CLTI classification system used (R or F), and num is the variable that contains the number of subjects with or without an event.

The results of the logistic regression are shown in **Table 6**. The classification system effect has a low p-value (p <0.0001) and an odds ratio (Rutherford 5 or 6 versus Fontaine IV) of 2.891.

Table 6: Results of Logistic regression predicting AFS using CLTI classification method

Analysis of Maximum Likelihood Estimates						
Parameter		DF	Estimate	Standard Error	Wald Chi-Square	Pr > ChiSq
Intercept		1	0.5020	0.0766	42.9900	<.0001
class	FIV	1	0.5308	0.0766	48.0546	<.0001
Odds Ratio Estimates						
Effect		Point Estimate	95% Wald Confidence Limits			
class FIV vs R56		2.891	2.141	3.903		

The 6-month AFS rates in studies shown in **Table 7** (reprint from Yale Clinical Research Group) that used the Fontaine classification were adjusted in two ways: a) the average of the percentage of Rutherford 5 or 6 in the other studies as reported in b) the odds ratio. The adjusted numbers were very similar between the two methods so for this document, the odds ratio adjusted numbers will be used. After the odds ratio adjustments,

STATISTICAL ANALYSIS PLAN

the final AFS rate point estimate was 42.0% with an upper 95% confidence limit of 51.2%. However, in acknowledgement of FDAs concern around the performance goal and the previous discussions since 2017, LimFlow is not proposing to change the previously communicated performance goal based on the prior Yale work where the AFS rate point estimate was 43.7%, with an upper 95% confidence limit of 53.5%. Since the hypothesis test for this study is a test for superiority, the performance goal is set at the upper 95% confidence limit (UCL) of 53.5%, rounded up to 54%.

**Table 7: Reprint of from YCRG:

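### The historical AFS of 42.3% (upper limit 51.1%) comes from using a hazard ratio as a ratio of survival proportions, so the claimed 2.9-point margin below the 54% goal is unsupported

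*Protocol*

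**What the plan says.** Protocol 11.2.2 adjusts each study's observed 6-month AFS to a Rutherford 5/6 (R5/6) population. The factor comes from three published hazard ratios (Table 5, titled "Publications reporting unadjusted HR for Rutherford Category 5/6 v. Rutherford Category 4"): "The resulting risk adjustment factor for AFS rates was 2.18". Equation 1 sets this hazard ratio equal to the ratio of event risks, (1 − High)/(1 − Low), and also to Low/High, the ratio of survival proportions. Equation 2 writes observed AFS as the mixture of the two groups. Equation 3 reads "Low Risk AFS = High Risk AFS/adjustment". Where a study gave no R5/6 share, "the proportion of high-risk patients was imputed based on the average of all studies that reported this proportion". The pooled result is 42.3% (33.5 to 51.1), and the protocol concludes: "The performance goal is set at 54%, which is 2.9% higher than the upper 95% confidence limit of 51.1" (per cent).

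SAP Appendix 1 gives a second table with 42.0% (32.8 to 51.2) and says that "for this document, the odds ratio adjusted numbers will be used". It traces the goal to earlier work in which "the AFS rate point estimate was 43.7%, with an upper 95% confidence limit of 53.5" (per cent), rounded up to 54%.

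**The concern.** The three terms of Equation 1 are different quantities. A hazard ratio of 2.18 does not mean that low-risk patients survive amputation-free 2.18 times as often. Since a proportion cannot exceed 1, that reading fails as soon as high-risk AFS exceeds 1/2.18 = 45.9%. It also pushes the R5/6 estimate down, which makes 54% look more demanding than it may be.

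In a single-arm trial, the historical rate is the only comparator. The protocol supports 54% by its position above the upper limit of that rate. If the limit is an artefact, exceeding 54% no longer leads to the conclusion that the device does better than historical care on the grounds given.

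**Working it through.** **Inputs.** N, event-free survivors and R5/6 share p come from Protocol Table 4 (21 studies, 1,017 patients) and SAP Table 7 (20 studies, 992 patients). Unreported shares are set to 66.0% and 66.9%, the simple means of the 12 and 11 reported shares. The hazard ratios are those of Protocol Table 5.

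**1. The factor.** Weighting log hazard ratios by sample size: exp[(98·ln 1.56 + 995·ln 2.3 + 281·ln 2.03)/1374] = 2.18. The study of death alone carries 995/1374 = 72% of the weight. Inverse-variance weights give 1.98. The only hazard ratio for AFS itself is 1.56.

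**2. The adjusted column.** Putting Low = 2.18 × High into Equation 2 gives High = observed/[p + (1 − p) × 2.18]. For the 177-patient study: 0.825/(0.66 + 0.34 × 2.18) = 58.9%, as printed. The formula matches all 21 rows of Table 4 within 0.06 points and all 20 rows of Table 7 within 0.05. Equation 3 as printed is inverted and would give 101.1% for this study; that is a wording slip which affected no tabled value.

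**3. The pooled figure.** DerSimonian-Laird pooling with variance High(1 − High)/N returns 42.3% (33.5 to 51.1) and 42.0% (32.8 to 51.2), exactly as stated.

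**4. What the formula implies.** Low-risk AFS is 2.18 × High, or 128% in the 177-patient study. It lies between 110% and 141% in 9 of the 19 mixed studies of Table 4 (666 of 971 patients), and above 100% in 8 of 18 in Table 7 (641 of 946). In each table, five of these rows (533 patients) use the imputed share, so their impossibility is conditional on it. Low-risk AFS exceeds 100% when p > (1 − observed) × 2.18/1.18, which is p > 32.4% for the 177-patient study and p > 44.9% for the 259-patient study.

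The other four Table 4 rows (133 patients) use reported shares. Equation 2 with every low-risk patient event-free gives the lowest possible R5/6 AFS, (observed − (1 − p))/p:

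| Survivors/N | p | Lowest possible | Printed |
|---|---|---|---|
| 66/79 | 63.3% | 74.0% | 58.3% |
| 8/10 | 80.0% | 75.0% | 64.7% |
| 14/19 | 65.0% | 59.5% | 52.1% |
| 21/25 | 56.0% | 71.4% | 55.3% |

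**5. Repairs.** Under proportional hazards, solve p·S^2.18 + (1 − p)·S = observed for low-risk AFS S, and take S^2.18 as the R5/6 rate. For the 177-patient study S = 0.896 and S^2.18 = 0.788 (check: 0.66 × 0.788 + 0.34 × 0.896 = 0.825), against 58.9% printed. Pooled as in step 3:

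| Adjustment | Table 4 | Table 7 | 54% minus upper limit |
|---|---|---|---|
| As printed | 42.3% (33.5–51.1) | 42.0% (32.8–51.2) | +2.9; +2.8 |
| (a) 2.18 as hazard ratio, all rows | 53.1% (39.5–66.7) | 52.0% (38.0–66.1) | −12.7; −12.1 |
| (b) All impossible rows capped at low-risk AFS = 100% | 47.0% (36.1–57.9) | 46.2% (35.0–57.5) | −3.9; −3.5 |
| (c) SAP odds ratio 2.891 on imputed-share rows, hazard ratio 2.18 on the rest | 45.3% (33.3–57.3) | 43.8% (31.7–56.0) | −3.3; −2.0 |
| (d) Hazard ratio on reported-share rows only | 47.7% (35.8–59.6) | 46.3% (34.2–58.5) | −5.6; −4.5 |
| (e) Cap on impossible reported-share rows only | 44.8% (35.1–54.4) | 43.7% (33.8–53.6) | −0.4; +0.4 |

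Rows (d) and (e) leave every imputed-share row as printed, so they are partial corrections.

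**6. Sensitivity.** For full repairs with the tables' own shares, hazard ratios 1.56 to 2.3 and six pooling choices (DerSimonian-Laird, Paule-Mandel and REML, on the raw and logit scales), upper limits run from about 54% to 68%. With the imputed share varied from 33.3% to 80.0% (the extremes reported by mixed studies), the hazard-ratio repair keeps upper limits between 58.6% and 69.2%. The cap in (b) depends on the share: its upper limit falls below 54% if the imputed share is under 52.4% (Table 4) or 55.0% (Table 7). I² after (a) is about 96%.

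**7. The SAP's description.** For the 177-patient study the odds are 146/31 = 4.71. Dividing by 2.891 gives 1.63, an AFS of 62.0%. Table 7 prints 59.3%, which is 0.825/(0.669 + 0.331 × 2.18). Table 7 therefore carries the 2.18 multiplication, not the odds-ratio adjustment described.

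**8. Reading a marginal pass.** SAP section 4 cut the maximum to 105 "After the N=90 but before the N=105 interim sample size assessments had occurred". With a Beta(1,1) prior and no missing data, the lowest passing result at N=105 is 67/105 = 63.8% (posterior probability 0.9779; 95% credible interval 54.3 to 72.4). That lies below the upper limit in (a), 66.7%, and above that in (b), 57.9%.

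**The case against.** The formula error is not in dispute. The strongest reply is that the criticised sentence is not where 54% came from: the SAP keeps a goal already communicated, resting on the earlier 43.7% and 53.5%. That stands as far as it goes. The earlier estimate has no study-level data in the documents, so it can be neither faulted nor relied on here, and it does not make the protocol's statement about 51.1% true.

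Second, the size of the correction is uncertain. The highest upper limits need proportional hazards, a factor dominated by one mortality study, and an imputed share in the largest studies. Repair (c) also assumes that the imputed-share rows are the Fontaine studies, although the protocol imputes for two kinds of study and does not say which row is which; the lowest limit in the 54% to 68% range comes from that repair. Under the narrowest correction, (e), the goal is still 0.4 points above the Table 7 limit. All of this argues for a range and against any single replacement figure, but it does not restore 2.9 points. The SAP odds ratio on imputed rows, with the faulty formula merely capped on the others, gives 52.3% and 51.3%; it keeps the error and is not a repair.

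Third, the plan has no criterion that compares the trial result with a historical upper limit. That is correct, and the N=105 comparison bears only on interpretation. Finally, the section summarises an external report, so correcting it may involve revising that report as well.

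**Conclusion.** The concern holds. The stated 42.3% (33.5 to 51.1) and 42.0% (32.8 to 51.2) reproduce exactly, but only through a formula that implies survival above 100% and contradicts Equation 2 in rows with reported shares. They are not valid estimates of historical R5/6 AFS. With 2.18 used as a hazard ratio, 54% is about one point above the Table 4 point estimate and 12.7 points below its upper limit. Under the smallest correction the margin is about zero (−0.4 or +0.4).

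These figures take the documents' 2.18 and shares as given, count all patients below R5/6 as low risk, and use DerSimonian-Laird pooling. Repairs (a), (c) and (d) also assume proportional hazards. The finding does not show that a different goal is right. What fails is the stated support for reading a result above 54% as better than historical care.

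**What to change.** 1. Correct Equations 1 to 3 in Protocol 11.2.2.
2. Recompute the adjusted columns of Protocol Table 4 and SAP Table 7 with the factor used as a hazard ratio, and re-pool. Report a range over hazard ratios 1.56 to 2.3, the imputed share (for example 33.3% to 80.0%) and the pooling method.
3. Make the SAP Appendix 1 text match the adjustment actually used in Table 7.
4. Withdraw the statement of a 2.9-point margin and give the recomputed range in its place.
5. Check whether the earlier 43.7% and 53.5% used the same formula, and say so.
6. Keep 54% as the pre-specified test value and word success as AFS exceeding 54%. Show the trial estimate and credible interval beside the recomputed historical range as a qualified interpretation, with no second pass/fail hurdle.

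The cost is a spreadsheet re-run and wording changes in both documents, and possibly a revision of the underlying meta-analytic report. Patients, test, thresholds and sample size do not change. The drawback for the sponsor is a historical comparison less favourable than the one now stated.

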**Table 5: Publications reporting unadjusted HR for Rutherford Category 5/6 v. Rutherford Category 4**

Study	N	Patient Risk Profile	Variable	Event	Unadjusted Hazard Ratio	95% CI
Chung et al. 2013	98	Rutherford 4/5/6	R 5/6 vs. R4	AFS	1.56	1.01 - 2.41
Soga et al. 2014	995	Rutherford 4/5/6	R 5 vs. R 4	Death	2.3	1.6 - 3.3
Spreen et al. 2016	281	Rutherford 4/5/6	Rutherford 5/6 vs. Rutherford 4	Major Amputation	2.03	1.28 - 3.21

**11.3 Determination of Sample Size**

Although the analysis methods are Bayesian, the following frequentist scenarios are used to guide the determination of minimum and maximum sample size.

- According to PASS 13, when using  $\alpha = 0.025$  (one-sided) in an exact binomial test, achieving 90% power to test the hypotheses in Section 7.1 when the true AFS = 0.70 would require a sample size of 101 subjects. Allowing for 10% missing data would require a sample size of N=113 subjects
- If the true AFS = 0.68, a sample size of 101 subjects would achieve 81% power. Allowing for 10% missing data would require a sample size of N=113 subjects
- If the true AFS = 0.75, 90% power requires a sample size of N=56 subjects. Allowing for 10% missing data would require a sample size of N=63 subjects.

There is considerable uncertainty in the true AFS rate  $\phi$ . Consequently, it is desirable to utilize a study design that achieves at least 80% power when  $AFS \geq 0.68$  and 90% power when  $AFS \geq 0.70$ , while allowing early stopping of enrollment if the AFS rate proves to be very high (e.g., 0.75) or very low ( $\leq 0.54$ ). Therefore, the study design was selected wherein the sample size is adaptively determined, with a minimum value of 60 and a maximum value of 120.

**11.4 Populations for Analysis**

**Modified Intention-To-Treat Population:** mITT is defined as all subjects where a LimFlow device was introduced into the patient, regardless of technical or procedural success or major protocol deviation.

**Per Protocol Population:** The Per-protocol (PP) population is defined as all subjects who met all inclusion/exclusion criteria and had a successful procedure.

**Untreated Population:** This population consists of all consented subjects who met all inclusion and exclusion criteria but are not included in the mITT population.

11.5 Statistical Analyses

11.5.1 General Approach

Descriptive statistics for continuous variables will include mean, standard deviation, median, quartiles, minimum, maximum, and sample size for each treatment group. Categorical variables will be summarized using counts and percentages. Proportions will be calculated using known non-missing values. Unless otherwise indicated, all statistical tests will be performed at  $\alpha=0.05$  (2-sided), and confidence/credible intervals will be at level 95%.

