#### 4.8 Secondary Endpoints

**Primary Patency:** Defined as absence of occlusion of the endovascular intervention that is maintained without the need for additional or secondary surgical or endovascular procedures, at 30 days and 6 months.

**Primary Assisted Patency:** Defined as absence of occlusion of the endovascular intervention that is maintained with the use of additional or secondary surgical or endovascular procedures, as long as occlusion of the primary treated site has not occurred, at 30 days and 6 months.

**Secondary Patency:** Defined as absence of occlusion of the endovascular intervention that is maintained with the use of additional or secondary surgical or endovascular procedures after occlusion occurs, at 30 days and 6 months.

**Limb Salvage:** Defined as percentage of subjects with freedom from above-ankle amputation of the index limb, evaluated at 30 days, 3 and 6 months.

**Change in Rutherford Classification:** Defined as a change of one class or greater, as evaluated at 30 days, 3 and 6 months.

**Technical Success:** Defined as the successful creation of an arteriovenous fistula in the desired limb location with immediate morphological success.

**Procedural Success:** Defined as the combination of technical success, and absence of all-cause death, above-ankle amputation or clinically driven major re-intervention of the stent graft at 30 days.

**Target Wound Healing:** Defined as complete healing of the patient's target wound as evaluated at 30 days, 3, 6, 9 months, and 1 year.

**All Wound Healing:** Defined as complete healing of the patient's wounds as evaluated at 30 days, 3, 6, 9 months, and 1 year.

**All Wound Area Reduction:** Defined as reduction in area of the patient's wounds as evaluated at 30 days, 3, 6, 9 months, and 1 year.

**Freedom from Contrast-Induced Nephropathy:** Defined as subjects without acute (within 72 hours after intravenous contrast administration) impairment of renal function, measured as an absolute  $\geq 0.5$  mg/dL (44  $\mu\text{mol/L}$ ) increase compared to baseline SCr value that results in a value above the upper limit of the normal range.

**Procedure Time:** Defined as the time of the first puncture (venous or arterial) to when the last catheter is removed.

**Radiation Exposure:** Defined as patient radiation exposure (in milligray) during the procedure.

**Contrast Volume:** Defined as the total volume of contrast media (in milliliters) given during the procedure.

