### 5.5 Enrollment (Day 0)

Once any component of the LimFlow System is introduced into the body, the subject will be considered to be enrolled in the study. If any LimFlow device is introduced but stent-graft implantation is either not attempted or unsuccessful, subjects will be followed for safety for 30 days with a minimum of phone calls to assess Primary Endpoint of AFS.

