### 5.9 Study Exit or Premature Withdrawal

Subjects will be exited from the study by completion of a Study Exit eCRF. Subjects will be exited upon completion of the follow-up visits, withdrawal of consent, or instance of meeting a primary study endpoint (major amputation or death). Following study exit, the subject will undergo the standard medical care for their condition as determined necessary and appropriate by their physician.

Subjects may be prematurely exited or withdrawn from the study for, including but not limited to, the following reasons:

- Voluntary withdrawal – meaning that the subject voluntarily chooses not to further participate in the study
- Lost to follow-up – meaning that the subject is more than 14 days out of window of a study visit and 3 documented attempts to contact the subject are unsuccessful. A subject who misses two consecutive study visits, including phone contact, will be considered lost to follow-up. A missed visit will be considered a protocol deviation and the deviation will be documented and reported.
- In the physician’s opinion, it is not in the best interest of the subject to continue study participation.

All subjects enrolled (including those withdrawn or lost to follow-up) shall be accounted for and documented.

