7 SECONDARY ENDPOINTS ANALYSIS

A listing of secondary endpoints is given in Section 3.2. Secondary endpoints will be evaluated with descriptive statistics, along with 95% confidence intervals computed using frequentist methods. No hypothesis tests will be conducted.

Methods:

- Secondary endpoints that are binary (e.g., technical success, freedom from contrast-induced nephropathy at 72 hours) will be summarized as a proportion, with a 95% confidence interval computed via an exact binomial calculation.

STATISTICAL ANALYSIS PLAN

- Secondary endpoints that involve the occurrence (or not) of events at times ≥ 30 days will be summarized with Kaplan-Meier time-to-event methods. Confidence intervals will be computed on the log(survival) scale.
- Continuous endpoints (e.g., procedure time, radiation exposure, contrast volume) will be summarized with means, medians, SD, quartiles, min, and max. Confidence intervals will be computed assuming approximate normality.

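### Change in Rutherford class is, on the natural reading, summarised only among subjects alive with the limb and still followed; neither document says how death or major amputation counts for it or for wound area

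*Protocol*

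**What the plan says.** **Denominator.** Protocol 11.5.1 gives a general default: "Proportions will be calculated using known non-missing values". It mentions neither death nor amputation. The SAP does not repeat it.

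**Exit.** Protocol 5.9: "Subjects will be exited upon completion of the follow-up visits, withdrawal of consent, or instance of meeting a primary study endpoint (major amputation or death". Under Protocol 5.5, when a device was introduced but no stent graft was implanted, "subjects will be followed for safety for 30 days with a minimum of phone calls to assess Primary Endpoint of AFS".

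**Endpoints.** Protocol 4.8 describes Change in Rutherford Classification as "Defined as a change of one class or greater, as evaluated at 30 days, 3 and 6 months", with no direction of change. All Wound Area Reduction is "Defined as reduction in area of the patient's wounds as evaluated at 30 days, 3, 6, 9 months, and 1 year", with no proportion or cut-off.

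**Methods.** SAP section 7 gives exact binomial intervals for binary endpoints. It also says: "Secondary endpoints that involve the occurrence (or not) of events at times ≥ 30 days will be summarized with Kaplan-Meier time-to-event methods". Continuous endpoints get descriptive summaries, and "Confidence intervals will be computed assuming approximate normality". It does not say which class Rutherford change or wound area falls into, and it takes its endpoint list from SAP 3.2. All Wound Area Reduction appears in the SAP synopsis but not in 3.2. Imputation is planned only for the primary endpoint.

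**The concern.** A subject who has died or lost the index limb has no later Rutherford class or wound area. That value is not missing in the ordinary sense, because the subject is known to have failed. A non-missing denominator nevertheless treats the two situations alike. The reported figure then describes a group selected on outcome, without saying so, and there is no control arm to show the selection.

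SAP 3.2 sets out to give a point estimate and its precision for each secondary endpoint. A reader would naturally take those estimates to describe the treated population (mITT), when they would describe only the part of it that kept life, limb and follow-up.

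**Working it through.** **1. Reproduce the planning curve.** SAP 6.7 gives daily hazards of 0.005417298, 0.00647187, 0.004045362 and 0.0015350038 over intervals of 30, 30, 30 and 90 days. The cumulative hazards are 0.1625, 0.3567, 0.4780 and 0.6162. S(t) = exp(−H(t)) gives 0.85, 0.70, 0.62 and 0.54 at days 30, 60, 90 and 180, as the SAP states.

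**2. Scale to other AFS values.** SAP 6.7 multiplies all hazards by k. It follows that S(t) = S0(t)^k with k = ln(AFS)/ln(0.54). (This is the power form implied by the scaling, not the product printed at the end of that SAP formula.) For AFS 0.70, k = 0.5788 and S(90) = 0.62^0.5788 = 0.758.

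**3. Observed-case factor.** Let r be the proportion improved among subjects alive with the limb. The observed-case figure is r. Counting death and amputation as not improved gives r × S(t). The ratio is 1/S(t), whatever r is. Loss to follow-up is set aside here as unrelated to outcome.

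| AFS at 180 days | S(30) | S(90) | S(180) | 1/S(90) | 1/S(180) |
|---|---|---|---|---|---|
| 0.54 | 0.850 | 0.620 | 0.540 | 1.61 | 1.85 |
| 0.70 | 0.910 | 0.758 | 0.700 | 1.32 | 1.43 |
| 0.75 | 0.927 | 0.800 | 0.750 | 1.25 | 1.33 |

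At AFS 0.70, death or amputation alone removes 1 − 0.758 = 24% by 3 months and 30% by 6 months.

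**4. How many remain assessable.** SAP 6.7 assumes 10% loss, uniform over 180 days, so the fraction not lost by day t is 1 − 0.10 × t/180. At AFS 0.70:
- 3 months: 0.758 × 0.95 = 0.72, about 76 of 105.
- 6 months: 0.70 × 0.90 = 0.63, about 66 of 105.

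At AFS 0.54 the fractions are 0.59 and 0.49. Subjects without an implant, who are followed for 30 days, would reduce these further; the documents give no rate for them.

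**5. Illustration.** The documents give no improvement rate. Assuming r = 0.60 at 6 months, the proportion with failures counted is 0.60 × 0.70 = 42% at AFS 0.70, and 0.60 × 0.54 = 32% at AFS 0.54. For r from 0.40 to 0.80 at AFS 0.70 it runs from 28% to 56%.

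**6. The Kaplan-Meier reading.** Assume visits at 30, 90 and 180 days, death and amputation censored, the same event risk whether or not a subject has improved, and 60% improved by 1 − KM. The per-visit conditional probability is q = 1 − 0.40^(1/3) = 0.263. The cumulative incidence with death and amputation as competing events is the sum of S(t) × (1 − q)^(i−1) × q over the three visits:
- AFS 0.70: 0.240 + 0.147 + 0.100 = 0.487.
- AFS 0.54: 0.224 + 0.120 + 0.077 = 0.421.

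So 1 − KM reads 60% against 49% or 42%. The bias is smaller than under the observed-case reading but in the same direction.

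**The case against.** The strongest reply is that the Protocol sentence is a general default, while SAP section 7 is the specific rule for secondary endpoints and can be read to put Rutherford change under Kaplan-Meier. Subjects would then stay at risk until censored and not be dropped. That reading is open, and it means the plan cannot be said to exclude these subjects expressly: the exclusion is inferred from Protocol 11.5.1 and 5.9 together. It does not remove the problem, as step 6 shows. Kaplan-Meier is also an awkward fit for a class difference that is read at fixed visits and can reverse.

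Four stronger readings are tempting and are not supported:
- **The non-missing sentence also governs wound area.** It concerns proportions, and wound-area reduction is not defined as one. The gap there is an absent rule.
- **The proportion would climb even if nobody improved.** With no improvers it is 0/n at every visit, whatever the denominator.
- **The endpoint would look better in a trial with worse AFS.** The factor 1/S(t) grows as AFS falls, but the reported figure also depends on r, which the documents do not give.
- **The plan reports an inflated benefit.** The Rutherford definition states no direction, so benefit is the reader's inference.

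It is also fair that these endpoints carry no hypothesis tests, that AFS and limb salvage are reported beside them, that counts and sample sizes are to be shown, and that individual listings are planned. Attrition can therefore be traced. Finally, a labelled summary among subjects alive with the limb is a legitimate estimand. The fault is that the plan neither chooses nor labels one.

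**Conclusion.** The point holds in this form. For Rutherford change, the Protocol text taken together yields a proportion among subjects alive with the limb and still followed. The alternative Kaplan-Meier reading also overstates improvement if death and amputation are censored. The 6-month observed-case factor is about 1.43 at AFS 0.70 and 1.85 at AFS 0.54. It rests on the SAP's planning hazards scaled proportionally and on loss unrelated to outcome; any specific improvement rate is an assumption.

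For All Wound Area Reduction the finding is a missing analysis rule and an omission from SAP 3.2. A mean over available values would carry the same survivor selection. Its size cannot be given from the documents, and the planning curve stops at 180 days while this endpoint runs to 1 year.

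A reader might infer that the trial's main conclusion is at risk. It is not: AFS counts both events, and the effect is confined to descriptive secondary estimates. The change should be made because it is cheap and those estimates will be read as results for the treated population.

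**What to change.** **Protocol 11.5.1.** Limit the non-missing rule to values that are truly unobserved.

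**SAP section 7, Rutherford change.** Assign it to a fixed-visit binary summary. State that the change counted is improvement by at least one class. Keep subjects with death or index-limb major amputation before the visit in the denominator as not improved.

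**SAP 3.2 and section 7, All Wound Area Reduction.** Add the endpoint to 3.2. Report the proportion alive with the limb and with reduced area, on the same denominator. Label any mean or median area change as being among subjects alive with the limb, and give its n.

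**Cost.** Wording in both documents and one more column in existing tables. No new data are needed, because deaths and target-limb amputations are already adjudicated by the Clinical Events Committee (Protocol 7.2). The downside is that the descriptive proportions become less favourable.
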